- Despite the large volume of platelet transfusions that they receive, the current platelet transfusion recommendations for children supported by ECMO are based solely on expert opinion (1).
- There is a huge knowledge gap (29,30) and no high-quality evidence to guide platelet transfusion practice in these children supported by ECMO (15).
- There is clearly equipoise with respect to platelet transfusion in pediatric ECMO patients (29).

In summary, platelet transfusions are widely used in children on ECMO (12) with little evidence to guide practitioners. There is no evidence that platelet transfusions are associated with improved outcomes; some data even suggest that platelet transfusion may be harmful (9). There is a need for a greater understanding of appropriate platelet transfusion strategies in these vulnerable children.

D. Hypotheses and Aims

This protocol pertains to the pilot clinical trial, which will evaluate the feasibility of randomizing a **LOW** platelet threshold transfusion strategy, in which a platelet count of $< 50 \times 10^{9}$ /L will trigger a platelet transfusion, compared to a **HIGH** platelet threshold transfusion strategy, in which a platelet count of $< 90 \times 10^{9}$ /L will trigger a platelet transfusion (Figure 3). We hypothesize that, in non-bleeding children on ECMO, a low prophylactic platelet threshold transfusion strategy is non-inferior to a high platelet threshold transfusion strategy, specifically related to bleeding or thrombotic complications, and this hypothesis is intended as a candidate primary hypothesis of the full RCT.

The objective of this pilot trial is to determine the feasibility of the full RCT through the following:

- Aim 1 is to demonstrate a separation between the LOWER and HIGHER platelet threshold transfusion arms. Specifically, we will demonstrate a difference in the average pre-transfusion platelet count between the two arms from randomization to when the treatment strategy was permanently discontinued. In addition, we will estimate the difference in average daily platelet dose during the same period, which we anticipate will be a difference of at least 20% between the groups randomized to each threshold.
- Aim 2 is to demonstrate the ability for observed endpoints to satisfy various prespecified feasibility thresholds. Specifically, there are 10 different criteria, and we will show that at least 5 of the 10 thresholds are satisfied by the estimated endpoints.

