The primary objective is to assess the separation between the higher and lower platelet threshold arms. Indeed, for a transfusion trial to be successful, there has to be a clinically meaningful separation between the transfusion strategies, to be able to imply causality for the outcome. Since the higher platelet threshold is $<90 \times 10^{9}$ /L and the lower platelet threshold is $<50 \times 10^{9}$ /L, we expect the **separation of the pre-transfusion platelet count (primary outcome) to be at least 30 x10⁹/L**. To assess the separation between both arms, we will collect the pre-transfusion platelet count before each transfusion event.

In addition, we will collect the total daily platelet transfusion dose for a patient while the patient is on ECMO. The average daily dose (in ml/kg/day) will be computed by the research team, by dividing the total platelet transfusion volume by the patient's weight at admission and the number of days on ECMO.

These outcomes will be measured outside of temporary suspensions; that is, transfusions occurring during a temporary suspension are ignored from these analyses.

The primary *safety* outcome, which is assessed in conjunction with the early trial stopping rule, is occurrence of any of the following from the time of randomization (enrollment) to 24 hours after the transfusion strategy threshold was permanently discontinued: progression from no bleeding or minimal bleeding to severe bleeding, according to the BASIC definition (34); severe thrombotic event, according to the NHLBI Hemostasis Clinical Trial Outcomes Working Group (need for circuit change, need for thrombectomy, ischemic stroke, or distal thromboembolism, as diagnosed clinically) (48); death (i.e., all-cause mortality). The primary safety outcome ignores severe bleeding/severe clotting that begins during a period of temporary suspension, but does not ignore deaths that occur during a period of temporary suspension.

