For the *pilot study*, the analysis of the primary outcome measure will be assessing the pretransfusion platelet count to describe the separation between the two platelet transfusion strategies, while accounting for intra-subject correlation. For each arm, we will estimate the mean pre-transfusion platelet count throughout the ECMO runs. This primary outcome will be measured for each transfusion and represent the latest available collected platelet count that is before the transfusion began. In the event that there was no preceding platelet count since a previous transfusion, the outcome for that transfusion will be regarded as missing. Participants who do not have a non-missing value for this outcome (e.g., they had no transfusions) will not be included in the analysis of the primary outcome. Because we anticipate intra-subject correlation when there are multiple transfusions for a patient, we will fit a linear model to pre-transfusion platelet counts with a fixed effect for assigned treatment (higher threshold vs. lower threshold). We will account for repeated measures by considering three within-subject covariance structures with constant variances: compound symmetry; the continuous analog of an autoregressive order 1 process, also known as CAR(1); and a hybrid of compound symmetry and CAR(1) achieved by including random subject effects and CAR(1) correlations in the within-subject errors. We will use restricted maximum likelihood (REML) for model estimation and use the model with the lowest Akaike Information Criterion (AIC) to select the best covariance structure. Once the covariance structure

is determined, the Kenward-Roger calculation for denominator degrees of freedom (df) will be applied in the F-test (equivalently, for the df in the t-test) of the treatment strategy's model coefficient. The test of the null hypothesis that the mean pre-transfusion platelet count is the same for each treatment arm vs the alternative that the higher threshold has a higher mean will be considered statistically significant if and only if the one-sided p-value is less than 0.025. In addition, a two-sided 95% confidence interval for the difference in means will be reported along with estimates of each treatment's mean and the difference in means, with all inferences coming from the repeated measures model described above.

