In addition, we will measure the effect of the days on ECMO, by providing summaries of the daily platelet counts for each specific ECMO day with \geq 5 patients still on ECMO, independent of receiving a platelet transfusion. This will allow evaluating trends over time and a possible attenuation of the separation over time.

Furthermore, we will also estimate the difference in the *median platelet transfusion dose* (in mL/kg/run) between the lower and higher platelet threshold strategy arms, and the median daily platelet transfusion dose (in mL/kg/day) to account for different lengths of ECMO runs. These outcomes will use two-sided nonparametric percentile bootstrap 95% confidence intervals, based on a minimum of 10,000 bootstrap replicates, for the difference in medians because by construction for each of these outcomes, there is only one outcome per person. As such, repeated measures modeling is not warranted.

Finally, we will also report the *screening and inclusion rates*, the proportion of patients who were *approached* within 24 hours of cannulation, the proportion of patients for whom we will be able to obtain *informed consent*, the number of *platelet transfusions prior to randomization*, the proportion of compliance with *transfusion thresholds*, number of *temporary suspensions*, and the ability to record data and *adjudicate bleeding and/or clotting outcomes*. In short, we will provide summaries of outcomes, with special emphasis for these summaries on the ten feasibility criteria of Aim 2.

Unless stated otherwise, the outcomes mentioned throughout the protocol are not intended to be tested for significance in this trial, but rather will be summarized descriptively (e.g., frequency and percentage for categorical variables, means and standard deviations or medians and interquartile ranges for continuous variables).

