5.5 Derived and Computed Variables

Derived variables needed for analysis will be defined in a corresponding data dictionary. Most variables of particular importance were already defined. Select variables of particular importance are defined in the remainder of this subsection.

Additional outcomes: transfusion volumes in mL/kg/run and mL/kg/day. These are the total platelet transfusion doses while on ECMO in mL/kg/run, and the transfusion dose in mL/kg/hr (or its redundant value, in mL/kg/day, obtained by multiplying the dose in mL/kg/hr by 24). When determining the total mL/kg of the platelet transfusions, all doses given from randomization until the permanent discontinuation of the transfusion strategy will be counted, whether or not the dose was transfused during a temporary suspension of the assigned strategy. The total transfusion dose measured in mL/kg/run is simply the mL/kg during this acute follow-up phase, whereas the dose in mL/kg/day is the total dose in mL/kg divided by the number of hours from randomization until permanent strategy discontinuation.

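### The supplementary daily platelet dose has two different time windows, and the documents give opposite rules for suspension transfusions in both the dose and the primary platelet count

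*Combined protocol and SAP*

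**What the plan says.** - **Protocol 5.D, Aim 1.** The pre-transfusion count is compared "from randomization to when the treatment strategy was permanently discontinued". For the dose, "we will estimate the difference in average daily platelet dose during the same period", with a difference of at least 20% anticipated. SAP 2.1.1 repeats this aim.
- **Protocol 9.A.** Here "we will collect the total daily platelet transfusion dose for a patient while the patient is on ECMO", and the average daily dose is the total volume divided by "weight at admission and the number of days on ECMO". For count and dose alike, "transfusions occurring during a temporary suspension are ignored from these analyses".
- **Protocol 9.B.** The closing paragraph again places count and dose, and feasibility criteria 1, 6 and 9, outside temporary suspensions.
- **Protocol 8.H.** Suspensions lead to exclusion from the analysis of one secondary endpoint only, criterion 6.
- **Protocol 10.C.** For the primary outcome, "we will estimate the mean pre-transfusion platelet count throughout the ECMO runs". The daily dose is reported "to account for different lengths of ECMO runs".
- **SAP 5.5.** Volume is counted from randomization to the permanent end of the strategy, including volume given during a suspension. The section ends by saying that "the dose in mL/kg/day is the total dose in mL/kg divided by the number of hours from randomization until permanent strategy discontinuation".
- **SAP 7.2 and 7.2.2.** The primary count uses the same window and includes suspension transfusions. The reason given for the daily dose scale is the varying duration of the strategy, not of the ECMO run.

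**The concern.** Protocol 9.A makes separation between the arms a condition for a successful transfusion trial, and the daily dose is the second way Aim 1 describes that separation. Once the strategy has ended, the assigned threshold no longer governs transfusion. ECMO days after that point, and days before randomization, carry no treatment contrast. Counting them pulls the arms together.

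Two analysts working correctly, one from protocol 9.A and one from SAP 5.5, would therefore report different dose separations. They would also treat suspension transfusions differently, and that second difference reaches the primary count and feasibility criterion 1.

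Appendix A builds its projected effect for the full trial on a reduction in exposure of at least 20%, to be confirmed in the pilot, so it matters which quantity the pilot estimates. The DCC statisticians are unblinded (protocol 8.F, SAP 3.3), so a choice between definitions made late could look data-driven.

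**Working it through.** **1. The definitions side by side.** Strategy window means randomization to the permanent end of the assigned strategy.

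| Place | Measure | Window | Suspension transfusions |
|---|---|---|---|
| Protocol 5.D, Aim 1 | count and dose | strategy window | not stated |
| Protocol 9.A | dose | days on ECMO | excluded |
| Protocol 10.C | dose | justified by ECMO run length | not stated |
| SAP 5.5, 7.2.2 | dose | strategy window | included |
| Protocol 9.A, 9.B | count | not stated | excluded |
| Protocol 10.C | count | ECMO runs | not stated |
| SAP 7.2 | count | strategy window | included |

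**2. When the windows differ.** Under protocol 8.G the strategy can end while ECMO continues: after severe bleeding or clotting, at day 21, after a suspension of more than 24 hours, or on withdrawal. Enrollment may also come up to 24 hours into ECMO (protocol 6.E). Protocol 11.A collects data daily to the end of ECMO, so the whole-run version can be computed.

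**3. Effect on the dose difference.** No stated figure in the plan depends on the daily dose formula, so there is none to reproduce. Inputs:
- the anticipated 20% difference (Aim 1), taken as true on strategy;
- higher-arm rate set to 10 units per day and lower-arm rate to 8 (arbitrary scale, ratio from the 20%);
- both arms at 10 units per day off strategy (assumption);
- S strategy days in a run of E = 10 ECMO days (assumption, varied).

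Lower-arm whole-run rate = (8S + 10(E − S)) / E. Apparent difference = 1 − that rate / 10 = 0.20 × S/E.

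| S of 10 days | Lower-arm rate | Apparent difference |
|---|---|---|
| 10 | 8.0 | 20% |
| 7 | (56 + 30)/10 = 8.6 | 14% |
| 5 | (40 + 50)/10 = 9.0 | 10% |
| 3 | (24 + 70)/10 = 9.4 | 6% |

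This illustrates rates in a typical course. The planned analysis compares medians, so the figures show direction and order of size only.

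**4. Suspension transfusions.** The documents do not say how many to expect, so this part cannot be sized. The direction is acknowledged in protocol 10.D, which notes that they may dilute separation. Criterion 1 requires an estimate above 30 × 10⁹/L, the same value the sample size assumes, so even a modest shift could decide it.

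**5. The unit in SAP 5.5.** Volume per kg divided by hours is mL/kg/hr. Take 92 mL/kg (the median total in protocol 5.B) over an assumed 7-day window: 92 / (7 × 24) = 0.548 mL/kg/hr, and 24 × 0.548 = 13.1 mL/kg/day. Over assumed windows of 5 and 21 days the pairs are 0.767 and 18.4, and 0.183 and 4.38. The factor is always 24. It applies to both arms and cancels from any relative difference.

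**6. Power.** The stated 81% follows from a difference of 30, an SD of 40 and an effective 30 observations per arm: 0.815 by the noncentral t, 0.828 by the normal approximation. The dose does not enter it.

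**The case against.** The best defence is that the intended window is recoverable. Aim 1 sits in the current protocol and agrees with the SAP, which governs the programming. For the primary count, SAP 7.2 states the window explicitly and criterion 1 takes its estimate from that model, so the phrase in protocol 10.C is loose rather than operative. The dose is not a primary outcome (SAP 2.2.1) and is in none of the ten feasibility criteria. All of this stands and limits the weight of the point. It does not reconcile protocol 9.A with Aim 1, and it does not touch the suspension conflict.

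A reader might also infer stronger things that the documents do not support:
- **That the later protocol (1.4, April 2024) overrides the SAP (November 2023, written against 1.3.1).** No precedence rule is stated, and protocol 1.4's own Aim 1 supports the SAP's window.
- **That results will be wrong by a factor of 24.** SAP 2.2.1, an earlier sentence of SAP 5.5, and SAP 7.2.2 all give the conversion.
- **That daily doses will differ by the ratio of ECMO days to strategy days.** That holds volume fixed, yet protocol 9.A also collects volume for as long as the patient is on ECMO. At a constant dosing rate the two definitions give the same daily dose. The problem is dilution of the contrast, not the level.
- **That the 65% event rate in Appendix A shows early stopping to be common.** It includes deaths, and a death on ECMO ends strategy and run together. It gives no timing, and Appendix A itself calls the data very uncertain.
- **That off-strategy transfusions will shrink the primary separation by a stated amount.** An analyst would have to set aside both Aim 1 and SAP 7.2, and the documents give no share of transfusions after discontinuation.

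**Conclusion.** The point holds as an inconsistency in definitions. Followed as written, protocol 9.A gives a whole-run daily dose whose between-arm difference is diluted relative to the one that Aim 1 and the SAP specify. A true 20% would read as 14%, 10% or 6% when the strategy covers 7, 5 or 3 of 10 ECMO days, if off-strategy dosing is equal in both arms at the higher arm's rate. With full coverage of the run there is no difference.

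The conflict over suspension transfusions is real for both dose and primary count and cannot be sized from the documents. It would persist after the windows were aligned. The loose window for the count in protocol 10.C and the missing factor of 24 are drafting slips whose intended meaning is clear elsewhere. The stated power is unaffected. The definitions should be settled before the final analysis.

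**What to change.** 1. In protocol 9.A, use the Aim 1 and SAP window, randomization to permanent strategy discontinuation, for both the volume counted and the time divided by. Admission weight can stay; SAP 5.5 should name it too.
2. In protocol 10.C, use the same window for the mean pre-transfusion count, and replace the reference to ECMO run lengths with strategy duration, as SAP 7.2.2 has it.
3. State one rule for transfusions during temporary suspensions, apply it to both dose and count, and make protocol 8.H, 9.A and 9.B and SAP 5.5 and 7.2 agree. Protocol 10.D already promises an analysis of how suspensions affect count separation, so results under the other rule can be shown there.
4. In the last sentence of SAP 5.5, write: mL/kg/day = 24 × total mL/kg / hours from randomization to permanent strategy discontinuation.

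The cost is a wording amendment to both documents. No new data, visits or sample size change are needed.

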H. Temporary suspension of Individual Patients

The protocol will allow for temporary suspensions, i.e., transfusion at a higher platelet count threshold than allowed for the randomization arm, if the clinical situation warrants immediate transfusion for certain conditions including: 1) chest-tube insertion; 2) surgical intervention while on ECMO (such as tracheostomy or repair of congenital diaphragmatic hernia); 3) during ECMO circuit change; or 4) in preparation for decannulation. In addition, while patients will be monitored for severe bleeding and/or severe clotting events during this time, they will not have the transfusion strategy permanently discontinued if they develop such an event during the temporary suspension, provided that the severe bleeding/clotting has resolved within the 24 hours of the temporary suspension. If a patient continues to have severe bleeding or severe clotting past the 24 hours of the temporary suspension, the intervention is stopped.

Adherence to the trial protocol must be resumed as soon as possible once these events are controlled or completed. Data monitoring and collection will be unchanged during suspension (including pre-transfusion platelet counts and platelet transfusion volumes), but data on length and justification of suspension will also be collected. Suspensions less than 24 hours will not be considered a breach of adherence to the protocol. After 24 hours of temporary suspension, the patient will have all assigned treatment strategy implications lifted (i.e., no restrictions on the range at which any subsequent platelet transfusions may occur) but will continue to be followed for ascertainment of safety and study outcomes. Temporary suspensions will only necessitate exclusion from analyses for one of the secondary endpoints (#6: proportion of compliant platelet transfusion actions), as explicitly noted in Section 9.B. The safety outcomes will still be followed but will be analyzed as a sub-group (e.g., severe bleeding during temporary suspensions).

9. Outcomes

The objective for the **pilot study** will be to assess the **feasibility** of the full RCT.

A. Primary Outcome

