The adjudication committee will evaluate patients who are deemed by site investigators to meet this endpoint (severe bleeding or clotting) in batches of 5 patients. The adjudicators will rotate, which will help prevent bias and ensure that all adjudicators have an equal opportunity to contribute to the study. We will report the inter-rater reliability (Kappa) at the end of the study. The committee will make determinations for whether bleeding was the primary cause of the worsening clinical outcome or if clotting was severe. Specifically, the sites will complete the severe bleeding/clotting daily worksheet (see Appendix E) on a daily basis. If a severe bleeding event, or clotting event, the event will be recorded in the database (and the intervention will stop for that participant since this safety outcome has been reached). Once five new patients have any of these events reported, the adjudication committee will review the events and report if they agree with the determination of the outcome within 72 hours of their review or if they need additional information from the site PI. Patient enrollment will continue during their reviews.

B. Secondary Outcomes

Our second objective is to demonstrate the ability for observed endpoints to satisfy various prespecified feasibility thresholds. The information the pilot trial will provide is both necessary and sufficient for the implementation of the full clinical trial. Based on PALISI and BloodNet's suggestions, we will seek further funding and progress to the full trial if at least 5 of the following 10 criteria are met:

- 1. Estimated separation in mean pre-transfusion platelet count is $> 30 \times 10^9$ cell/L;
- 2. Eligibility rate is > 50% of the predicted eligibility rate of 7.9 patients per site per year;
- Proportion of patients whose parents were approached for consent within 24 hours of cannulation (number of patients approached / number of patients eligible for consent) > 90%;
- Proportion of patients for whom we were able to obtain informed consent (number of patients consented / number of patients approached) > 50%;
- 5. Randomization of consented patients is > 66%;

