 It will be possible to consider the pilot ECSTATIC trial as a vanguard phase of the full RCT and to merge their data to the data of the patients enrolled in the full trial if no significant changes are made to the design of the full RCT. On the other hand, merging patients of the pilot and the full trials would be inappropriate if significant changes are made (e.g., the threshold platelet count is changed). In that case, we will combine the data of the pilot and of the full RCT by performing a meta-analysis.

11. Study Monitoring and Study Organization

Approval for use of this protocol by the Human Studies Committee (HSC) must be obtained in accordance with the institutional assurance policies of the U.S. Department of Health and Human Services. Institutional Review Board (IRB) approval of the ECSTATIC protocol and consent forms will be required prior to patient participation on the trial. The single IRB at BRANY will coordinate IRB approvals at each site within the United States. All reasonable measures will be taken to protect the confidentiality and identity of the patient and patient's records according to State and Federal laws. Patient identity will not be revealed in any publication.

A. Study Monitoring

Data will be collected at PICU entry (e.g., PRISM and PELOD-2 scores, co-morbidity, coagulation evaluation, etc.), at ECMO cannulation, at randomization, daily while patient is on ECMO, at ECMO end, and at PICU discharge. Data will be collected at least on a daily basis from ECMO initiation to ECMO end. Mortality (28-day and 90-day) is the only data that would be collected after PICU discharge. The application of the RCT protocol (lower or higher platelet threshold strategy) will end at the earliest of any of the following five events: (1) progression to severe bleeding, according to the BASIC definition, and/or severe clotting, and/or death; (2) decannulation from ECMO; (3) Twenty-one days post-randomization (as the progression to new bleeding and new thrombosis has plateaued by day 21 and 95% of the patients will be off ECMO by then); 4) temporary suspension lasting more than 24 hours; or 5) study withdrawal.

Data management will include an audit trail, a security system, query functionality and quality control done according to US CFRs. Data management will be performed at the Trial Innovation Network at the University of Utah under the supervision of the study statistician.

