2.2.5 Safety Outcome(s)

Many safety outcomes are obtained during the *acute follow-up period*, defined as the period beginning with randomization and ending 24 hours after the permanent discontinuation of the transfusion strategy. The transfusion strategy for a randomized patient is permanently discontinued at the earliest of any of the following five events: (1) per site report, progression to severe bleeding, according to the BASIC definition, and/or severe clotting, and/or death; (2) decannulation from ECMO; (3) twenty-one days post-randomization (as the progression to new bleeding and new thrombosis has plateaued by day 21 and $\approx 95\%$ of the patients will be off ECMO by then); 4) temporary suspension lasting more than 24 hours; or 5) study withdrawal.

The primary safety outcome is defined at the patient level for all patients in the ITT population. It is defined as the occurrence of any of the following during the acute follow-up period: progression to severe bleeding (defined below); progression to severe thrombosis (defined below); death. The outcome is initially site-reported but then is to be adjudicated by the adjudication panel. If the panel determines the outcome criteria were not met, the outcome will be considered not to have occurred. Otherwise, if the panel confirms the criteria were met, or if the panel is unable to reach a determination, the primary safety outcome will be considered to have occurred.

Using the BASIC definition [2], severe bleeding will be defined as:

- 1. Bleeding that leads to at least one organ dysfunction, using PELOD-2 score criteria of organ dysfunction
- 2. Bleeding that leads to hemodynamic instability, defined as an increase in heart rate (HR) by > 20% from baseline or a decrease in blood pressure (BP) by > 20% from baseline (i.e., prior to the bleeding event)
- 3. Bleeding leading to a drop in hemoglobin >20% within 24hr
- 4. Quantifiable bleeding $\geq 5 \text{ mL/kg/hr}$ for $\geq 1 \text{hr}$ (e.g., chest tube)
- 5. Intracranial hemorrhage on computerized tomography (CT) scan or head ultrasound
- 6. Intraspinal bleeding leading to loss of neurologic function below the lesion, nontraumatic intra-articular bleeding leading to decreased range of movement, or intraocular bleeding leading to impaired vision.

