5.2 Methods for Withdrawals, Missing Data, and Outliers

Participants who withdraw from the study intervention should continue to be followed for assessment of safety outcomes, if allowed. However, outcomes such as the primary outcome of pre-transfusion platelet counts and adherence to study intervention will be ignored from analyses beginning at the time of the withdrawal.

Because the outcomes generally relate to adherence or outcomes that should have no missingness (e.g., whether or not a patient consented), it is not expected that missing data will be problematic for the main analyses. There is naturally some protection against detrimental effects due to missing data for model-based analyses that incorporate random effects or other forms of within-subject correlation, such as for the primary outcome.

Outliers may affect the primary analysis because the primary analysis of Aim 1 is meanbased. Pre-transfusion platelet counts that appear to be outliers may be queried to ascertain if the values were correctly recorded. If it is determined that the values were not correctly recorded, they will be corrected if the correct values are available. If it is determined the values were not correctly recorded but the correct values are unavailable, the platelet counts will be regarded as missing for the primary Aim 1 analysis of separation in mean platelet counts.

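### An overturned site report still closes the primary safety window, so a later severe event or death on ECMO goes uncounted; other early exits are also scored on a shortened window

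*Combined protocol and SAP*

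**What the plan says.** **Window.** Protocol 9.A runs the primary safety outcome from randomization "to 24 hours after the transfusion strategy threshold was permanently discontinued". SAP 2.2.5 defines the acute follow-up period in the same way, "ending 24 hours after the permanent discontinuation of the transfusion strategy", and scores the outcome for every ITT patient. Neither text has a censoring rule or an extension.

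**What ends the strategy.** SAP 2.2.5 lists five events. The first is severe bleeding, severe clotting or death per site report; the second and third are decannulation and day 21. The list ends "4) temporary suspension lasting more than 24 hours; or 5) study withdrawal". A site report, a long suspension and a withdrawal can all happen while the child is still on ECMO.

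**Order of report and adjudication.** Under Protocol 9.A, once a site records a severe event, "the intervention will stop for that participant since this safety outcome has been reached". The panel reviews later, when five new patients have accumulated. SAP 2.2.5 then says: "If the panel determines the outcome criteria were not met, the outcome will be considered not to have occurred". A report the panel cannot resolve counts as an event.

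**Follow-up.** Protocol 8.H says that a child whose strategy is lifted after 24 hours of suspension has no further transfusion restrictions "but will continue to be followed for ascertainment of safety and study outcomes". SAP 5.2 says: "Participants who withdraw from the study intervention should continue to be followed for assessment of safety outcomes, if allowed". Protocol 11.A says: "Data will be collected at least on a daily basis from ECMO initiation to ECMO end". The Protocol Abstract (Subject Participation Duration), however, ends daily follow-up 24 hours after the strategy expires.

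**Use.** The outcome feeds the two-sided Fisher tests at 0.0333 in Protocol 10.C (Interim Analysis) and SAP 6.4. It is also one of several inputs to the full trial's design (Protocol 10.A).

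**The concern.** The overturned-report rule gives a wrong score when followed exactly as written. Suppose a child is reported on day 2, the panel later overturns the report, and the child has a confirmed stroke or dies on ECMO on day 8. The report ended the strategy on day 2, so the window closed on day 3. The report is then scored as not having occurred, and nothing reopens the window or sends the day-8 event to the panel. The child enters the safety test as event-free.

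The exits through long suspension and withdrawal raise a milder form of the problem. Their shortened window may be intended, but it fits poorly with the statements that safety follow-up continues, and no analysis is defined for what that follow-up finds.

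At stake is the only formal safety test in the trial. Mortality at 28 and 90 days and ELSO-defined complications are collected, but only for description; they enter no test.

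**Working it through.** **1. The plan's own boundaries.** Inputs: Protocol 10.C example, 1:1 arms, half of the enrolled children with the outcome, two-sided Fisher p ≤ 0.0333. The exact test reproduces all five pairs for the lower arm: 0 or 5 of 5; ≤2 or ≥8 of 10; ≤4 or ≥11 of 15; ≤6 or ≥14 of 20; ≤8 or ≥17 of 25.

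**2. Effect of one lost event at a boundary.**

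| Counted events | p | After one lower-arm event is lost | p |
|---|---|---|---|
| 14 v 6 of 20 | 0.026 | 13 v 6 | 0.056 |
| 17 v 8 of 25 | 0.023 | 16 v 8 | 0.046 |
| 9 v 17 of 25 | 0.046 | 8 v 17 | 0.023 |

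A lost event can therefore remove a signal of harm (first two rows) or create a significant difference (third row).

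**3. When an overturn becomes known.** Take the planned 50 children over 24 months and the roughly 65% rate of severe bleeding, clotting and/or death in Protocol Appendix A (Sample Size). Reports then arrive at 0.65 × 50 / 24 = 1.35 per month. The first child in a batch waits for four more, 4 / 1.35 = about 3 months on average, before review starts. The strategy lasts at most 21 days, so for most children other than the last in a batch the ruling will come after the ECMO run. The lost period cannot be recovered at that point unless the site kept assessing severe events.

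**4. How many events could be missed (illustrative).** Let p be the true event rate, f the share taken off the strategy early while on ECMO, and m the share of their events falling after the window. Then observed rate = p × (1 − f × m), and missed events per 50 children = 50 × p × f × m. The documents give neither f nor m.

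- *m:* assume a constant hazard reaching 65% by day H, so hazard = −ln(0.35)/H. With H = 10 and the strategy lifted on day 5, the probability of an event by day 6 is 0.467 and m = 1 − 0.467/0.65 = 0.28. With H = 21 and lifting on day 2, the probability by day 3 is 0.139 and m = 0.79. I use 0.3 to 0.8.
- *f:* feasibility criteria 7 and 8 (Protocol 9.B) tolerate under 10% with a non-decannulation suspension of any length and under 6% withdrawn or lost. Their sum, 16%, is an upper guide for those two exits. Overturned reports are not quantified; Protocol 10.C expects them to be uncommon.

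| f | Observed rate (true 65%) | Missed per 50 |
|---|---|---|
| 5% | 64.0% to 62.4% | 0.5 to 1.3 |
| 10% | 63.0% to 59.8% | 1.0 to 2.6 |
| 16% | 61.9% to 56.7% | 1.6 to 4.2 |

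**5. Effect on the stopping rule (illustrative).** The SAP Appendix simulation, re-coded, gives an average type I error of 0.049 against the stated 0.0502. With assumed true rates of 80% (lower arm) and 50% (higher arm), 4,000 simulated trials per scenario and m = 0.5, the probability of a significant test is:

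- full follow-up: 0.55
- f = 10% in each arm: 0.48
- f = 16% in each arm: 0.44
- f = 16% lower, 5% higher: 0.38

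**The case against.** The strategy-plus-24-hours window is used consistently: in the Protocol Abstract, 9.A and the adverse event sections, and in SAP 2.2.2 (SE10) and 2.2.5. It is a defensible choice. The rule asks whether following a threshold causes harm, and once the strategy is lifted, transfusion is unrestricted, so later events partly reflect off-strategy care. SAP 8 says the pilot is not powered for this outcome. Later deaths and ELSO complications are still summarized by arm, the DSMB sees arm-level data in closed session, and under the current protocol a significant test leads to a pause and DSMB review. For exits through suspension and withdrawal this stands: nothing requires the sponsor to replace the on-strategy window as the main analysis.

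It does not answer the overturned report. There the strategy ended because of an event the trial later ruled had not occurred, yet the child keeps the shortened window and the non-event score.

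Three stronger readings are tempting and are not supported:

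- *Events are lost mainly from the lower arm, which would make it look safer.* The listed suspension reasons in Protocol 8.H are procedural, SAP 2.2.2 (SE7) does not require an above-threshold transfusion for a suspension to count, and nothing says long suspensions will be commoner in one arm.
- *The loss is large.* No document gives the number of early exits, the feasibility limits are low, and undeterminable reports already count as events.
- *The loss should be judged against the 5-point non-inferiority margin.* That margin belongs to the future trial, whose primary outcome excludes death.

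**Conclusion.** The point holds in limited form and should be fixed. As written, an overturned site report both ends observation and scores the child as event-free, so a later severe event or death on ECMO cannot enter the formal safety test. Exits through long suspension or withdrawal are scored on a similarly short window, which is defensible as an on-strategy analysis but unreconciled with the promised follow-up.

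That much follows from the text: a binary outcome, all ITT patients, a fixed window and no rule to reopen it. An event or death within the extra 24 hours still counts. Size and direction by arm are unknown. Roughly one missed event per 50 children at 5% early exit is plausible under the assumptions shown, and the larger figures use the sum of two feasibility ceilings. The practical consequence is confined to tests near a boundary, where one event is enough to cross 0.0333. Confidence is high on the wording and moderate on the size.

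**What to change.** 1. In Protocol 9.A and SAP 2.2.5, state that an overturned report does not close the outcome window. For that child the window runs to 24 hours after the earliest of decannulation, day 21, death, or a confirmed or undeterminable severe event, and any later site-reported event goes to the panel.
2. Prespecify, for the DSMB and the final report, a supporting analysis by assigned arm that counts severe bleeding, severe thrombosis and death to 24 hours after decannulation or day 21, whatever the strategy status, where follow-up is allowed. The on-strategy window can stay as the main analysis if the sponsor prefers.
3. Reconcile the continued follow-up in Protocol 8.H and 11.A and SAP 5.2 with the closing point in the Protocol Abstract, Protocol 9.A and SAP 2.2.5.

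None of this alters a threshold, a suspension rule or when the strategy stops.

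Cost: wording changes, plus more site work than a few worksheets. Because rulings come late, the Appendix E worksheet must continue to ECMO end for site-reported children until they are adjudicated, as well as for other early exits. At the 65% planning rate up to about 0.65 × 50 = 32 children could have a report, fewer in practice because that rate includes deaths and some children leave ECMO soon. Daily data are already due to ECMO end. Some interim outcomes will be determined later, and so enter the Fisher tests later. In the supporting analysis, post-strategy events will dilute the contrast somewhat. No window recovers events in a child whose family refuses follow-up.
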